#### **Secondary Objectives:**

To assess the effect of treprostinil on the following cardio-pulmonary parameters:

- the rate of rise of systemic venous pressures,
- pulmonary blood flow
- dynamic vascular functional responses including pulse wave velocity, brachial flow mediated dilatation, and venous structure and function (venous structure and function only performed at visit 1, pre-baseline exercise).
- The degree of liver stiffness at rest and the acute rise in liver stiffness induced by exercise

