#### Secondary Research Hypotheses:

- Inhaled treprostinil will increase peak VO2 relative to placebo
- Inhaled treprostinil will decrease ventilatory equivalent for CO2 at the lactate threshold (VE/VCO2 at LT) and at peak exercise relative to placebo.
- Inhaled treprostinil will result in a higher estimated lactate anaerobic threshold relative to placebo
- Inhaled treprostinil will result in a superior oxygen uptake efficiency slope
- Inhaled treprostinil will result in an increase in pulmonary blood flow. We hypothesize that this effect will be more pronounced in patients noted to have a

more elevated rate of rise in systemic venous pressures with exercise at baseline relative to placebo

- Inhaled treprostinil will improve exercise related changes in rate of rise of systemic venous pressures
- Inhaled treprostinil will result in improved vascular function tests, specifically pulse wave velocity, and brachial flow mediated dilatation.
- Higher resting venous pressures will be associated with a greater degree of liver stiffness, and greater rises in venous pressures will induce proportional rises in liver stiffness
- Inhaled treprostinil will attenuate the degree of exercise induced acute liver stiffness

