  - If systolic BP drops below 90 mm Hg or drops  $\geq$  30 mm Hg from the baseline for visit 2/visit 3, the participant's blood pressure will be monitored until return to above these thresholds.
  - Study staff monitoring the blood pressure will consult with the PI or MD subI should a drop in blood pressure meeting these thresholds occur. Patient will continue with the investigation at the discretion of the PI or MD subI.
- Venous pressure manometer set-up (including calibration) will then be conducted prior to commencing exercise testing during which the venous pressures will be measured continuously during the exercise test.
- Maximal exercise testing/Ramp protocol (including spirometry).
- Immediately following exercise, a shear wave liver elastography will be repeated
- Post recovery, vascular function assessment (FMD and PWV) will be repeated.
- Light meal followed by a break for complete exercise recovery
- If the participant tolerated the prior dose of treprostinil or placebo, (i.e no clinically significant AEs deemed by the PI or MD subI to be related to study drug that would preclude the patient from continued participation) they will receive a 3rd dose of their assigned treatment.

- If the patient did not experience a significant drop in blood pressure (as defined previously) following the prior dose, then no further blood pressure monitoring will be required prior to the exercise test.
- If the participant experienced a drop in blood pressure following the previous dose, then blood pressure will be monitored for  $\frac{1}{2}$  hour (immediately, 15 min, and 30 min.) following the 3rd dose of treprostinil or placebo.
  - If systolic BP drops below the thresholds described previously, the participant's blood pressure will be monitored until return to above these thresholds.
  - Study staff monitoring the blood pressure will consult with the PI or MD subI should a drop in blood pressure meeting these thresholds occur. Patient will continue with the investigation at the discretion of the PI or MD subI.
- Endurance exercise test at 80% peak exertion to occur 2 hours after the maximal exercise testing. This is expected to last about 4-7minutes.
  - Venous pressures will be measured during the exercise test as described herein (see Venous Cannulation).
- The participants will be observed for 60 minutes following medication administration.
- Adverse event monitoring

The visit is anticipated to take 5-6 hours.

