### **Visit 3 (Visit 3 will occur 1-2 weeks (+/- 3 days) after Visit 2.)**

- Study participants will be asked to repeat the study protocol described under Visit 2, and at that time, they will be crossed over to either active drug treatment or placebo, depending on their assigned treatment sequence.

Study staff will contact the participant approximately 2 weeks after visit 3 to assess for adverse events.

Table 1 presents the schedule of procedures for this study.

Table 1.

	Visit 1	Visit 2 and Visit 3						
		Prior to Dose 1	Dose 1	Immediately After Dose 1	Dose 2	Immediately After Dose 2	10 minutes after Maximal Exercise Test	Dose 3
Elapsed Time								
Procedures:								
Informed consent	X							
Demographics and medical history	X	X d						
Concomitant Medication Review	X	X						
Vital signs	X	X		X f		X f		X f
Resting ECG		X						
Urine pregnancy	X	X						
Randomization	X							
Administer Drug			X		X			X
Venous Pressure a						X		X
Spirometry	X c					X c		
Vascular Function (FMD/PWV)				X			X e	
Shear Wave Elastography				X			X (immediate post max exerc test)	
Maximal Exercise Ramp Test	X e					X		
Venous Structure and Function	X							
Exercise Endurance Test	X							X
Complete Metabolic Panel b , Once only, at visit 2 or 3		X						
CBC, GGT Once only at visit 2 or 3		X						
Adverse Event Monitoring	X	X	X	X	X	X	X	X

a. Venous pressure will be measured from before exercise test, every 1 minute during exercise, until 5 minutes after exercise. Cannula for venous pressure may be placed early in the day to facilitate scheduling.

b. Complete metabolic panel will include: sodium, potassium, chloride, carbon dioxide, BUN, creatinine, calcium, glucose, albumin, total protein, AST, ALT, ALP, and total bilirubin.

c Spirometry will occur prior to maximal exercise test.

[figure not shown]
d Prior to exercise testing, if medical history or adverse event questioning reveals intercurrent chest infection, wheezing, or other respiratory condition, study staff will consult with PI or designee to determine if exercise testing should proceed.

e Patients will be given a light meal during visit 1 and after the 2nd vascular test is completed at visits 2 and 3.

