### **Venous Cannulation**

An 18 gauge catheter will be placed in each participant's antecubital vein and will be connected to a pressure monitor. Venous pressures will be monitored prior to beginning exercise and then every minute during exercise and after exercise during the recovery period (5 minutes). Venous pressures measured using a peripheral venous line has previously been shown to be reflective of central venous pressure in Fontan patients (Milhoan et al., 2004).

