## Maximal Exercise Testing/Ramp Protocol

The {ParvoMedics Exercise cart with Blue Cherry software} will be used for cardiopulmonary exercise testing in all cases. The equipment will be calibrated and operated to the standards specified in the ATS/ACCP (2003) guidelines. Participants will initially sit at rest on the electromagnetically-braked cycle ergometer for three minutes while baseline cardiopulmonary variables are recorded (baseline phase). This will be followed by three minutes of unloaded cycling at a cadence of 60 rpm, after which the power output will be increased by 15 Watts per minute until the limit of tolerance. Talking to the study subjects will be kept to a minimum. Participants will be asked to maintain a cadence of 60 rpm throughout the test until volitional intolerance. The power output will be immediately reduced to zero and the cardiopulmonary variables monitored for at least 5 minutes (recovery phase). Transcutaneous CO2 monitoring will be done throughout the exercise test. Venous pressures will be monitored during exercise as described above (see Venous Cannulation).

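### Venous pressure on the ramp test is both continuous and once a minute in the protocol, and the once-a-minute rule schedules no end-exercise reading on either test

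*Combined protocol and SAP*

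**What the plan says.** Section 6, Visit 2, describes manometer set-up immediately before the maximal (ramp) test and adds that "venous pressures will be measured continuously during the exercise test". Visit 3 repeats the Visit 2 procedures.

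Section 6, Venous Cannulation, has pressures taken before exercise and then "every minute during exercise and after exercise during the recovery period", with recovery given as 5 minutes. Table 1 footnote a says "every 1 minute during exercise, until 5 minutes after exercise"; the venous pressure row is marked for both the ramp and the endurance occasions. The ramp section refers back to Venous Cannulation, and so does the endurance bullet in the Visit 2 list.

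On use of the data, Section 3 lists "the rate of rise of systemic venous pressures" among the secondary objectives and hypothesises that "greater rises in venous pressures will induce proportional rises in liver stiffness". The Endurance Exercise Testing section plans an isotime comparison that includes venous pressure. Post-exercise elastography follows the ramp immediately. Neither Section 9.1 nor Section 9.2 lists venous pressure or says how a rate of rise is calculated.

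**The concern.** Two operators could each follow the protocol on the ramp and produce different data. In a two-period crossover, a change of practice between Visits 2 and 3 enters the within-participant contrast. Because rate of rise is undefined, the recording rule goes a long way towards deciding what that outcome is.

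The once-a-minute rule has two consequences of its own. It gives few points for a slope, and it guarantees no pressure at the moment exercise stops. That moment is the natural partner of the post-ramp stiffness reading and of the peak-exercise pulmonary blood flow. Individual values matter as well: Section 2.3 intends to use pressure responses to classify responders, and Section 10.1 provides for informing a participant's cardiologist of lower venous pressures. Averaging over 26 participants does not reduce measurement error in those uses.

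**Working it through.** **Which rule applies where.**

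| Test (Visits 2 and 3) | Continuous | Once a minute |
|---|---|---|
| Ramp | Visit 2 set-up step | Venous Cannulation (by cross-reference); Table 1 footnote a |
| Endurance | not stated | Venous Cannulation (by cross-reference); Table 1 footnote a |

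The contradiction is confined to the ramp.

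**The plan's own figure.** Section 9.3 gives an SD of 65 s, a difference of 37 s, two-sided 0.05, 80% power and 26 patients. Normal approximation: n = [65 × (1.960 + 0.842) / 37]² = 24.2, so 25. The t-based calculation gives 27, with 79.7% power at 26. The figure reproduces and does not involve venous pressure. The documents give no SD or power for venous pressure.

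**End-exercise gap.** Both tests end at the limit of tolerance, so I take the stopping time as uniform within a minute. The gap from the last whole-minute reading then runs from 0 to just under 60 s, with mean 30 s, and is 30 s or more in half of tests. At the ramp's 15 W per minute this is 0.5 × 15 = 7.5 W below peak on average and up to 15 W.

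If pressure rises linearly over T minutes (an assumption), the rise is understated on average by 0.5/T:
- endurance, 4 to 7 min: 0.5/4 = 13% to 0.5/7 = 7%;
- ramp, assumed 8 to 10 min (the documents give no ramp duration): 6% to 5%.

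**Slope precision.** Let s be the SD of noise in one reading. With minute readings at 0, 1, …, T, SE = s/√Sxx. For T = 4, Sxx = 10 and SE = 0.32s per minute from 5 points. For T = 7, Sxx = 42 and SE = 0.15s from 8 points. Readings every 5 s stand in for a continuous trace; with independent noise they give 0.12s and 0.05s.

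The documents give neither s nor how long the noise persists, so I varied the correlation time. Ratio of slope SEs, minute readings to 5-second readings, by ordinary least squares:

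| Correlation time | 4 min | 5.5 min | 7 min | 10 min |
|---|---|---|---|---|
| independent | 2.61 | 3.15 | 2.91 | 3.05 |
| 5 s | 1.82 | 2.19 | 2.01 | 2.10 |
| 10 s | 1.38 | 1.63 | 1.49 | 1.55 |
| 30 s | 0.98 | 1.13 | 1.02 | 1.05 |
| 60 s | 0.91 | 1.02 | 0.93 | 0.95 |

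Ratios below 1 arise because ordinary least squares is inefficient with correlated noise. With generalised least squares the 30 to 60 s rows become 1.01 to 1.21. These figures also take each minute value to be a spot reading, which the documents do not say.

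**Effect on the treatment comparison.** If a fraction f of the variance of the treatment difference in slope is sampling noise under the minute rule, and r is the SE ratio, the SD of that difference is inflated by 1/√(1 − f + f/r²). For assumed f = 0.10 and r = 1.5 this is 1.03; for f = 0.50 and r = 3 it is 1.34.

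**Effect on the pressure-stiffness association.** The gap has SD 1/√12 = 0.289 min, so on an 8 to 10 min ramp the error SD is 0.289/T, or 3.6% to 2.9% of the rise. If the rise has a between-participant coefficient of variation of 20% to 40% (assumed), the regression slope shrinks by about (0.036/0.20)² = 3% down to (0.029/0.40)² = 0.5%.

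**The case against.** The best defence is that the sections can be reconciled: the manometer displays pressure continuously and staff write down a value each minute. That is ordinary practice and may be what was meant, but the protocol does not say so. It would still leave no scheduled end-exercise value unless a test happened to stop on a whole minute, or the first recovery reading were taken at time zero, which is not stated.

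Other points on that side stand:
- Whole-minute readings at both visits supply matched times for the isotime comparison, so that analysis is not shown to be harmed.
- A missing last reading does not bias a fitted slope. The average under-read of a rest-to-peak rise has the same cause under drug and placebo and largely cancels, although its random part does not. A late plateau in pressure would shrink it.
- Venous pressure is secondary in a pilot study, and its undefined rate of rise is a larger gap than the sampling interval.

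A reader might infer that the trial already holds a recorded trace and discards most of it. The documents do not support that: they describe a pressure monitor and continuous measurement, but no storage or export. A reader might also infer that both tests carry conflicting rules; only the ramp does.

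**Conclusion.** The conflict on the ramp is real and should be reconciled. So should the absence of a scheduled end-exercise pressure on either test. That absence follows from the text and depends on no noise assumption; its mean of 30 s assumes only that stopping times are spread evenly within the minute.

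The loss of slope precision is conditional. The SE ratio is about 1.4 to 3.2 if noise has a correlation time up to about 10 s, and close to 1 if noise lasts 30 to 60 s. It would be wrong to read this as a two- to threefold loss in the treatment comparison, because true visit-to-visit variation dilutes it by an amount the documents do not allow one to calculate. The weakening of the pressure-stiffness association is probably small. The primary endpoint, the sample size of 26 and the isotime comparison at whole minutes are not affected.

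**What to change.** - Make the Visit 2 procedures, Venous Cannulation and Table 1 footnote a state one recording rule, and say whether each reported value is a spot reading or an average.
- Where the monitor can export it, keep the continuous trace for both tests at Visits 2 and 3. Minute values can be derived from a stored trace later; the reverse is impossible.
- Add a time-stamped end-exercise pressure just before load is removed. On the ramp, also record its timing relative to the Innocor manoeuvre, which involves a mouthpiece change and about half a minute of rebreathing at peak exercise.
- Add venous pressure to Section 9.1 and pre-specify rate of rise in Section 9.2 as a within-participant slope over the exercise time common to both visits. A slope of short-epoch means is one reasonable choice. Use the rest to end-exercise rise on the ramp for the pressure-stiffness analysis.

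The cost is protocol wording and slightly more data handling. Whether the existing monitor can export a trace has to be checked. The end-exercise value on the ramp may be disturbed by rebreathing, which is why its timing should be recorded.

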### Baseline visit (Visit 1)

- Informed Consent
- Review of Demographics, Medical history, and Medications
- Urine pregnancy testing (for females of childbearing potential)
- Baseline vitals (heart rate, blood pressure, oxygen saturation, height and weight)
- Maximal cardiopulmonary exercise testing/Ramp protocol (including spirometry).
- Venous structure and function testing
- Light meal and rest period.
- Endurance testing at 80% peak exertion to assess baseline measures. (2 hours following maximal exercise testing)
- Adverse event monitoring

Visit 1 is anticipated to take 5-6 hours to complete. At the end of Visit 1, participants will be randomized to one of the two treatment sequences:

1. Treprostinil (Visit 2): placebo (Visit 3) or
2. Placebo (Visit 2): treprostinil (Visit 3).

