## **Endurance Exercise Testing**

Exercise endurance is a highly sensitive measure of functional outcome following interventions (Oga et al., 2000; Borel et al., 2013). Two hours after ramp incremental exercise testing (CPET) a constant work rate exercise test will be performed to determine exercise endurance; 2 hours is sufficient for complete recovery of exercise endurance following prior exhaustive exercise (Ferguson et al., 2010). The primary outcome from this assessment is exercise duration; standard CPET variables will also be measured throughout to provide physiological interpretation for exercise endurance change. A power output corresponding to 80% of the peak power achieved during the ramp incremental test will be calculated. After ~ 3 minutes at unloaded cycling, the power will be increased abruptly to 80% peak power: The subject will be encouraged to continue for as long as possible and the duration recorded. The target duration for this exercise test at baseline is 4-7 minutes and is typically achieved at 80% peak power (van der Vaart et al., 2013). In the event that the exercise endurance test duration falls outside of this 'optimal' range at the first visit, the power output may be adjusted by 5 Watts (or 10% rounded to the nearest 5W, whichever is greater) and this adjusted power used for all subsequent tests.

Exercise endurance change, and well as change in "isotime" physiologic variables (comparison between physiologic values during active drug and placebo measured at the same time points during exercise), including central venous pressure and vo2, between tests with placebo and inhaled treprostinil will be calculated.

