## **9. DATA ANALYSIS**

### **9.1. Study Endpoints**

The primary endpoint is exercise endurance time (seconds).

The secondary endpoints are the following:

- Peak VO2
- Ventilator equivalent for CO2 at the lactate threshold
- Oxygen uptake efficiency slope
- Lactate threshold
- Pulmonary blood flow
- Pulse wave velocity
- Augmentation Index
- Shear wave elastography (measure in velocity [m/s]), the mean of 10 measurements will be taken.
- Safety endpoints will include: a drop in systolic systemic blood pressure of greater than 30 mm Hg if SBP >120mm Hg, or a drop in BP to <90 mm Hg if resting BP is less than 120mmHg.

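### Does the plan leave open which work rate the endurance test uses at Visits 2 and 3?

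*Combined protocol and SAP*

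**What the plan says.** The load for the endurance test is described in two kinds of place in the combined protocol and SAP.

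- **Visit lists (section 6).** Visit 1 has "Endurance testing at 80% peak exertion to assess baseline measures". Visit 2 has "Endurance exercise test at 80% peak exertion to occur 2 hours after the maximal exercise testing", followed by "This is expected to last about 4-7minutes". For Visit 3, "Study participants will be asked to repeat the study protocol described under Visit 2".
- **Endurance Exercise Testing (section 6).** The general rule is "A power output corresponding to 80% of the peak power achieved during the ramp incremental test will be calculated". There is one exception. If the first-visit test lasts less or more than the 4-7 minute target, the power may be "adjusted by 5 Watts (or 10% rounded to the nearest 5W, whichever is greater) and this adjusted power used for all subsequent tests". The section also plans an isotime analysis, a "comparison between physiologic values during active drug and placebo measured at the same time points during exercise".

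Table 1 shows a ramp test at all three visits. Those at Visits 2 and 3 come after the second dose of study treatment. Section 9.1 makes endurance time in seconds the primary endpoint. The ANOVA in section 9.2 has terms for sequence, subject nested in sequence, and treatment, and none for work rate.

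**The concern.** Endurance time at a constant work rate depends on the work rate, so a crossover comparison in seconds needs each participant to face the same load on drug and on placebo. Two things seem to threaten that.

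First, the Visit 2 line gives 80% without exception, while the detailed section carries an adjusted load forward. A participant adjusted at Visit 1 is no longer at 80% of the Visit 1 peak, so the two places appear to prescribe different loads.

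Second, for participants who were not adjusted, the readable text speaks only of the ramp test without naming the visit. Two of the three ramps are done on study treatment. If the load were taken from the same-day ramp and the drug raised peak power, the drug-visit test would be harder than the placebo-visit test. The difference in seconds would then be biased toward no effect, and the model has no load term to correct it.

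**Working it through.** **1. The plan's own figure.** Inputs from section 9.3: SD of the treatment effect 65 s, difference 37 s, two-sided alpha 0.05, power 80%, 26 patients. Treating 65 s as the SD of the within-patient difference:

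n = (SD × (z₀.₉₇₅ + z₀.₈₀) / difference)² = (65 × (1.960 + 0.842) / 37)² = 4.92² = 24.2, so 25 patients.

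The noncentral t version gives 27, and power with 26 is 79.7%. The stated 26 is therefore reproduced. Work rate does not enter this calculation.

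**2. Size of the permitted adjustment.** Let L be 80% of Visit 1 peak power. The step is the larger of 5 W and 10% of L rounded to the nearest 5 W, taking the 10% to mean 10% of the load. The documents give no peak powers, so those below are assumed.

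| Assumed peak (W) | L (W) | Step (W) | Lowered (W, % of peak) | Raised (W, % of peak) |
|---|---|---|---|---|
| 60 | 48 | 5 | 43, 71.7% | 53, 88.3% |
| 100 | 80 | 10 | 70, 70% | 90, 90% |
| 150 | 120 | 10 | 110, 73.3% | 130, 86.7% |

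These departures from 80% are what the plan's exception is meant to produce. They do not measure an error, and they cancel within a participant when the same wattage is used at both treatment visits.

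**3. Adjusted participants.** The Endurance Exercise Testing section holds both the rule and the exception, and its carry-forward to all later tests covers Visits 2 and 3. The visit lists restate only the rule. The Visit 2 expectation of 4-7 minutes is the range the adjustment aims for, so it fits the carried-forward load better than a return to a load already found out of range.

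**4. Participants not adjusted.** The readings side by side:

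- *Same-day ramp.* Both the Visit 2 line and the opening of the Endurance Exercise Testing section place the endurance test two hours after a ramp. Both statements are mainly about timing and recovery.
- *Visit 1 ramp.* The duration target is set at baseline, adjustment is allowed only at the first visit, and the adjusted load is then held. The isotime analysis compares drug and placebo at equal exercise times, which isolates treatment only if the load is equal. Under the same-day reading, adjusted participants would keep a fixed load while the rest had theirs reset at each visit, and nothing in the plan suggests two such regimes.

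**5. Effect on the treatment contrast.**

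- One wattage at both treatment visits: the load component of the within-participant difference is zero.
- Wattage differing for reasons unrelated to treatment: noise, under randomised and blinded sequences.
- Wattage recalculated from an on-treatment ramp, with a drug effect on peak power: bias. The ramp rises 15 W per minute, so one extra minute would raise a recalculated load by 0.80 × 15 = 12 W. The documents give neither a drug effect on peak power nor a conversion from watts to seconds, so this cannot be turned into a bias in seconds.

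**The case for a change.** The best case for a change is that the load is a measurement condition of the primary endpoint, that the visit list is what staff have in hand on the day, and that the on-treatment ramp is performed two hours before the endurance test. A coordinator could take 80% of that morning's peak in good faith. The carry-forward sentence covers adjusted participants only, so for the rest the fixed load is an inference. A one-sentence clarification would cost almost nothing.

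Part of this stands. The readable text does not name the ramp for participants who were not adjusted, and a same-day load would matter if it were used. It is less certain that the plan as a whole is silent: the headings for Visit 1 and for Visits 2 and 3 after Medication Administration have no text beneath them in this copy, so visit schematics may have been lost there.

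The claimed contradiction does not stand. A checklist line that omits an exception spelled out in the section defining the test does not prescribe a competing load. The remaining harm depends on staff taking a step that no readable sentence directs and that would spoil the planned isotime analysis.

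**Conclusion.** No change to the plan is needed. For adjusted participants the documents already settle the load. For the others there is a narrow gap in wording, which a reader of the whole Endurance Exercise Testing section fills with a single Visit 1 wattage per participant. Under that reading the within-participant comparison of endurance time is sound as planned, no stated figure changes, and 26 patients remain consistent with 80% power for 37 s. Writing the rule out would record what the plan implies without altering the design or the analysis.

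The conclusion assumes that the same wattage is used at Visits 2 and 3 for each participant. It would fail if loads were in fact recalculated from the on-treatment ramps and the drug altered peak power; the documents do not allow the size of that effect to be estimated.
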